5.4.3. Management of Hyperphosphatemia

Hyperphosphatemia is an expected on-target pharmacologic effect of FGFR inhibition. Hyperphosphatemia should be managed with diet modifications, phosphate binders and diuretics, or a dose reduction per the recommendations in [Table 3](#). **Note for Japan:** Phosphate binders are not approved for the treatment of increases of serum phosphate caused by an FGFR inhibitor. When phosphate binders are used, the binders must be tracked in a drug accountability ledger that includes lot number. This drug accountability ledger will be monitored in the same way the study drug ledger is reviewed.

Table 3: Recommended Approach for Hyperphosphatemia Management

Serum Phosphate Level	Supportive Care	Guidance for Interruption/Discontinuation of INCB054828	Guidance for Restarting INCB054828
> 5.5 mg/dL and ≤ 7 mg/dL	Initiate a low-phosphate diet.	No action.	Not applicable.
> 7 mg/dL and ≤ 10 mg/dL	Initiate/continue a low-phosphate diet and initiate phosphate-binding therapy once serum phosphate level is > 7 mg/dL. Monitor serum phosphate at least twice a week and adjust the dose of binders as needed; continue to monitor serum phosphate at least twice a week until return to normal range.	If serum phosphate level continues to be > 7 mg/dL and ≤ 10 mg/dL with concomitant phosphate-binding therapy for 2 weeks, or if there is recurrence of serum phosphate level in this range, interrupt INCB054828 for up to 2 weeks (not including the planned dose interruption per treatment cycle).	Restart at the same dose when serum phosphate is < 7 mg/dL. If serum phosphate level recurs at > 7 mg/dL, restart INCB054828 with dose reduction.
> 10 mg/dL	Continue to maintain a low-phosphate diet, adjust phosphate-binding therapy, and start/continue phosphaturic agent. Continue to monitor serum phosphate at least twice a week until return to normal range.	If serum phosphate level is > 10 mg/dL for 1 week following phosphate-binding therapy and low phosphate diet, interrupt INCB054828. If there is recurrence of serum phosphate level in this range following 2 dose reductions, permanently discontinue INCB054828.	Restart INCB054828 at reduced dose with phosphate binders when serum phosphate is < 7 mg/dL.

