Study Schedule/Procedures:

Subjects will have regularly scheduled study visits at the clinical site as part of a 21-day cycle. Study visits are as follows:

- **Prescreening:** To obtain FGFR status, if unknown (results within 2 years of screening are valid for this study).
- **Screening:** Day -28 through Day -1.
- **Cycle 1:** Days 1, 8, and 15 (weekly visits for the first cycle).
- **Cycles 2+:** Day 1.
- **End of Treatment (EOT).**
- **Safety follow-up:** 30 days (+ 5 days) from date of last dose.

Local Laboratory Tests:

Study visits will include sample collection for hematology, chemistry, coagulation, endocrine monitoring, lipid panel, and urinalysis testing. Additionally, hepatitis screening (serology) will be done at screening, and pregnancy testing for women of childbearing potential will be done at screening, Day 1 of every cycle before dose administration, and EOT. FGF/FGFR status may be determined locally for screening/enrollment.

Central Laboratory Tests:

Tumor tissue will be evaluated at the sponsor's central laboratory for confirmation of FGF/FGFR alteration status. [REDACTED]

Clinical Assessments:

Adverse event assessments, vital signs, electrocardiograms, physical examinations, ECOG performance status, comprehensive eye examinations, and tumor and disease response assessments will be performed by the investigative site.

An objective assessment of disease status will be performed at screening. Subsequently, disease status will be assessed per RECIST every 9 weeks until start of new anticancer therapy, disease progression, death, or end of study. A central radiology group will be contracted to provide centralized reading on all assessments.

Duration of response will be assessed from the date of the first confirmed response to the date of the first documented evidence of disease progression or death. Progression-free survival will be assessed starting from date of first dose and then every 9 weeks until disease progression or death. Overall survival will be assessed from the first dose until death (every 12 weeks from disease progression to death).

Estimated Duration of Participation:

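### Read literally, Protocol Table 3 can interrupt study drug up to about a week later for a phosphate recurrence first seen above 10 mg/dL than for one at 7 to 10 mg/dL

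*Protocol*

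**What the plan says.** Table 3 (Protocol Section 5.4.3) sets out supportive care, interruption or discontinuation, and restart by phosphate level. Its title and column headings present it as recommendation and guidance.

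**Row > 7 to ≤ 10 mg/dL.** There are two triggers for interruption:
- persistence: "If serum phosphate level continues to be > 7 mg/dL and ≤ 10 mg/dL with concomitant phosphate-binding therapy for 2 weeks"
- recurrence: "or if there is recurrence of serum phosphate level in this range". No waiting time is attached.

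The restart cell of this row adds: "If serum phosphate level recurs at > 7 mg/dL, restart INCB054828 with dose reduction".

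**Row > 10 mg/dL.** Interruption has one trigger, persistence: "If serum phosphate level is > 10 mg/dL for 1 week following phosphate-binding therapy and low phosphate diet". The only recurrence clause is for permanent discontinuation: "If there is recurrence of serum phosphate level in this range following 2 dose reductions". Supportive care is stepped up as soon as the level is in this row: "adjust phosphate-binding therapy, and start/continue phosphaturic agent". Restart is at a reduced dose.

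Both rows ask for phosphate at least twice a week, but only until the level is back in the normal range. After that, the schedule in Section 6 applies. In Cycles 2 onward, serum chemistries, which include phosphate (Table 6), are required on Day 1 ± 3 days of each 21-day cycle (Table 5).

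**The concern.** A table tiered by severity should not respond more slowly to a worse value. Here the recurrence trigger is tied to a band with an upper limit of 10 mg/dL, and the row above that limit has no matching trigger until two dose reductions have been made. A subject with no or one earlier reduction whose recurrence is first seen above 10 mg/dL falls between the two clauses and gets only the 1-week rule.

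The stake is subject safety and consistent practice across up to 100 sites (Section 4.3). The primary endpoint and its analysis are not affected. The gap is most relevant to Cohort A-CD, which has no planned off-week. In the Phase 1 study, hyperphosphatemia at 13.5 mg was reported in 14 of 15 subjects (93.3%) on continuous dosing and 38 of 50 (76%) on interval dosing (Table 1). Those counts are for any level and do not show how often 10 mg/dL is exceeded.

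**Working it through.** The plan states no figure on this point, so the check is to apply Table 3 literally and then look for another rule that closes the gap.

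**1. Recurrence, the two rows side by side**

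| Recurrence first seen at | Earlier dose reductions | Literal action |
|---|---|---|
| > 7 to ≤ 10 mg/dL | any | interrupt, no stated wait |
| > 10 mg/dL | 0 or 1 | interrupt only after 1 week above 10 mg/dL |
| > 10 mg/dL | 2 | permanently discontinue |

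The second line is out of order with the first and third.

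**2. Timing.** Assume 0 or 1 earlier reductions, binders and diet from day 0, and checks on days 0, 3 and 7.

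| Course of the recurrence | Interruption day |
|---|---|
| 8 mg/dL, whatever follows | 0 |
| 10.5 mg/dL and stays there | 7 |
| 10.5 mg/dL, then 9 mg/dL at day 3 | 3 (now a recurrence in the lower band) |
| 10.5 mg/dL, then 6.5 mg/dL at day 3 | none |

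The largest delay against the 8 mg/dL case is 7 − 0 = 7 days.

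**3. Doses in those 7 days**
- Continuous regimen: 7 doses. 7 × 13.5 mg = 94.5 mg, or 7 × 9 mg = 63 mg after one reduction.
- Intermittent regimen (Days 1 to 14 on, Days 15 to 21 off): detection on Days 1 to 8 gives 7 doses. The count falls to 0 for detection on Day 15 (Days 15 to 21 are all off) and rises to 6 for Day 21 (one off day, then Days 1 to 6 of the next cycle). The range is 0 to 7.

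**4. Can a recurrence first be seen above 10 mg/dL?** Yes. Monitoring is stepped up only up to a point: "continue to monitor serum phosphate at least twice a week until return to normal range". After that, two Day 1 checks with ± 3 days each are 21 − 6 = 15 to 21 + 6 = 27 days apart in Cycles 2 onward. A rise through the 7 to 10 band can pass unseen in that time. If a value in the band is seen first, interruption is already triggered and there is no delay.

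**5. Does another rule close the gap?**
- Table 2 (Section 5.4.2) interrupts for Grade 3 toxicity that is clinically significant and cannot be managed with supportive care, and stops drug for Grade 4. Section 8.1.2 has hyperphosphatemia graded on symptoms and intervention rather than on the phosphate value, so a result above 10 mg/dL does not trigger Table 2 by itself.
- Section 5.4.5 allows stopping on the judgment of the investigator or medical monitor, with no phosphate threshold.
- The restart cell's > 7 mg/dL wording has no upper limit, but it sets the dose at restart and does not say when to interrupt.

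None of these supplies a phosphate-level rule for this case.

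**The case against.** The strongest case on the other side is that this is a drafting omission that few clinicians would act on. The restart cell speaks of recurrence > 7 mg/dL with no ceiling, and a restart presupposes an interruption. An investigator told to interrupt at 8 mg/dL is unlikely to think the table forbids it at 10.5 mg/dL. The table is advisory, and during the week in question binders are adjusted, a phosphaturic agent is started or continued, and phosphate is checked at least twice weekly. The case is also narrow: an earlier episode that resolved, fewer than two reductions, and a first recurrent value above 10 mg/dL. All of this stands and limits the weight of the point. It does not remove the gap, because the written rule still acts later on the worse value.

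A second objection is that closing the gap has a price. A recurrence above 10 mg/dL that would settle by day 3 would be interrupted and restarted at a reduced dose, using up one of the two recommended reductions. Section 5.4.2 leans the other way for transient, symptom-free laboratory values of up to 72 hours. That cost is real, but the table already accepts it for a recurrence at 8 mg/dL.

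Three stronger readings are tempting but not supported:
- **A delay of 17 days.** This arises if a fall from 10.5 to 9 mg/dL on day 3 is held not to be a recurrence in the lower band, so that a new 2-week count starts (3 + 14 = 17). After an earlier resolved episode, 9 mg/dL is most naturally a recurrence in that band, so day 3 applies.
- **Demonstrated harm.** The mineralization caution in Section 5.6.1 concerns calcium-based binders. In Section 1.3.1, soft tissue mineralization in rats did not reverse over 28 days, but it also did not progress and was judged a likely exacerbation of a spontaneous condition. The 28-day monkey study found none. Nothing ties an extra week above 10 mg/dL under escalated treatment to harm in subjects.
- **A fault in the 2-week count.** A subject who first crosses 10 mg/dL on days 10 to 14 of a first episode would be interrupted on days 17 to 21, against day 14 for one who stays at 8 mg/dL. Crossing 10 mg/dL starts stronger treatment, so allowing time for it to work is defensible.

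**Conclusion.** The point holds as a minor correction to a safety rule. Followed literally and before two dose reductions, Table 3 can act up to about 7 days later on a recurrence first seen above 10 mg/dL than on one at 7 to 10 mg/dL.

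This rests on a literal reading of an advisory table, on the first recurrent value being above 10 mg/dL, and on the level staying there for the week. The delay is shorter, or absent, if the level falls, if a 7 to 10 value is seen first, or if the investigator acts on judgment. After two reductions the gap does not exist. The documents do not give the proportion of subjects who exceed 10 mg/dL. For scale only, each 1% of Cohort A-CD (n = 100) would be 1 subject.

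**What to change.** Make the recurrence trigger for interruption match the > 7 mg/dL threshold of the restart cell. Either edit is enough:
- in the > 7 to ≤ 10 mg/dL row, replace the reference to recurrence in this range with *recurrence of serum phosphate level > 7 mg/dL (including > 10 mg/dL)*; or
- in the > 10 mg/dL row, add to the interruption clause *or if there is recurrence > 10 mg/dL after an earlier episode > 7 mg/dL had resolved to ≤ 7 mg/dL*.

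The restart dose is reduced in either row, so the restart cells need no change. Leave the permanent-discontinuation rule as it is and add no words that give it priority. Its two-reduction limit already sits awkwardly with the three reductions that Section 5.4.5 allows after up-titration, and firmer wording would make that worse. Leave the 2-week count unchanged.

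The cost is one phrase in one cell, by amendment or clarification letter, with no extra visits or tests. There would be a few earlier interruptions with a reduced-dose restart, including some recurrences that would have settled within a week. The table was aligned with the other INCB054828 protocols at Amendment 4 (Appendix C), so the wording would differ from theirs unless they are changed too.

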5.4.4. Up-Titration

Any subjects treated at 13.5 mg QD will be titrated up to 18 mg QD using their current dose regimen with approval from the medical monitor if they meet the following criteria:

- Have been on study drug for at least 1 cycle.
- Have been compliant with taking study drug.
- Have no ongoing Grade 2 or higher treatment-related AE.
- Have not achieved hyperphosphatemia defined as a serum phosphate level of > 5.5 mg/dL.

Subjects who are titrated up to 18 mg QD will begin the next cycle at the new dose level and must agree to all Cycle 1 assessments (████████ safety assessments [hematology and blood chemistry]). Up-titration may occur no earlier than Cycle 2 Day 1, so that subjects are observed for phosphate level and AEs for at least 1 cycle.

For subjects who are up-titrated from 13.5 mg to 18 mg, dose reductions are allowed (see Section 5.4.2).

5.4.5. Criteria for Permanent Discontinuation of Study Drug

The occurrence of unacceptable toxicity not caused by the underlying malignancy will be presumed to be related to study drug treatment and will require that the study drug be permanently discontinued. Unacceptable toxicity is defined as follows:

- Occurrence of an AE that is related to treatment with the study drug that, in the judgment of the investigator or the sponsor's medical monitor, compromises the subject's ability to continue study-specific procedures or is considered to not be in the subject's best interest.
- An AE requiring more than 2 dose reductions (unless dose has been up-titrated, then 3 dose reductions are allowed).
- Persistent AE requiring a delay of therapy for more than 21 days unless a greater delay has been approved by the sponsor.
- Increase in QT/QTcF to > 500 milliseconds or to > 60 milliseconds over baseline.

5.5. Withdrawal of Subjects From Study Treatment

5.5.1. Withdrawal Criteria

Subjects **must** be withdrawn from study drug for the following reasons:

- The subject becomes pregnant.
- Consent is withdrawn. Note: Subjects may choose to discontinue study treatment and remain in the study to be followed for progression and survival.
- Further participation would be injurious to the subject's health or well-being, in the investigator's medical judgment.
- The study is terminated by the sponsor.
- The study is terminated by the local health authority, IRB, or IEC.
- Unacceptable toxicity has occurred
- Disease progression has occurred

A subject **may** be discontinued from study treatment as follows:

- If, during the course of the study, a subject is found not to have met eligibility criteria, the medical monitor, in collaboration with the investigator, will determine whether the subject should be withdrawn from the study.
- If a subject is noncompliant with study procedures or study drug administration in the investigator's opinion, the sponsor should be consulted for instruction on handling the subject.

5.5.2. Withdrawal Procedures

In the event that the decision is made to permanently discontinue the study drug, the last date of the last dose of study drug and the reason for subject withdrawal will be recorded in the eCRF.

In addition, the following steps should be followed (Note: These visits are described in Section 6):

- The study monitor or sponsor must be notified.
- The reason(s) for withdrawal must be documented in the subject's medical record and in the eCRF.
- The EOT visit should be performed.
- The date of the EOT visit should be recorded in the IRT.
- Subjects must be followed for safety until the time of the follow-up visit or until study drug-related toxicities resolve, return to baseline, or are deemed irreversible, whichever is longest.

If the subject discontinues study treatment and actively withdraws consent for collection of follow-up data (safety follow-up or disease assessment), then no additional data collection should occur; however, subjects will have the option of withdrawing consent for study treatment but continuing in the follow-up period of the study for safety/efficacy assessments.

5.6. Concomitant Medications

5.6.1. Restricted Medications

The use of mild or moderate CYP3A4 inhibitors or mild CYP3A4 inducers should involve careful monitoring. Use of calcium-based phosphate-binding medications while on study is cautioned due to a concern for soft tissue mineralization.

5.6.2. Prohibited Medications

The following medications and measures are prohibited:

- The concomitant administration of potent CYP3A4 inhibitors and inducers and moderate CYP3A4 inducers is prohibited. Based on the low overall bioavailability of topical ketoconazole, there are no restrictions on topical ketoconazole.
- Any concomitant use of a selective FGFR inhibitor is prohibited.
- Investigational study drug for any indication is prohibited.
- Use of any anticancer medications other than the study medication from 21 days before Day 1 is prohibited.

6. STUDY ASSESSMENTS

All study assessments will be performed as indicated in the schedule of assessments (Table 4), and all laboratory assessments will be performed as indicated in Table 5. Table 6 presents a summary of clinical laboratory analytes to be assessed. The order of assessments is suggested by the order of mention within the schedule. See Section 7 for instructions on each assessment. Further details of study procedures and assessments can be found in the study reference manual.

Table 4: Schedule of Assessments

Procedure	Protocol Section	Pre-Screening	Screening Days -28 to -1	Treatment				EOT	Follow-Up			Notes
				Cycle 1		Cycles 2+			Safety EOT + 30-35 Days	Disease Status Every 9 Wks	Survival Every 12 Wks	
				Day 1	Day 8 (± 3 Days)	Day 15 (± 3 Days)	Day 1 (± 3 Days)					
Informed consent	7.1		X									
Eye examination (includes slit lamp, visual acuity, fundoscopy with digital imaging, and OCT)	7.5.5		X				X*	X				* Eye examination to be performed every 3 cycles (± 14 days) starting with Cycle 3 and/or as clinically indicated.
Review inclusion/ exclusion criteria	3		X	X								
Demography and medical history	7.3		X									
Prior/concomitant medications	7.4		X	X	X	X	X	X	X			
Physical exam/ body weight, height	7.5.2		X*	X	X	X	X	X	X			* Comprehensive examination at screening, targeted examination thereafter. Height at screening only.
Vital signs	7.5.3		X	X	X	X	X	X	X			
12-lead ECG	7.5.4		X	X		X	X	X	X			
ECOG status	7.6.2		X	X	X	X	X	X	X			
CT or MRI	7.6.1		X				X*	X		X**		* Every 9 weeks (every 3 cycles starting at the end of Cycle 3) if measurable disease is present. ** Subjects who discontinue study treatment for a reason other than disease progression.
Review AEs	8		X	X	X	X	X	X	X			
Study drug dispensing	5.2			X			X*					* Assess for up-titration (see Section 5.4.4).
Survival status	6.4.3										X*	* Once a subject has received the last dose of study drug, confirmed disease progression, or starts a new anticancer therapy.

CT = computed tomography; MRI = magnetic resonance imaging.

Table 5: Schedule of Laboratory Assessments

Laboratory Tests	Protocol Section	Screening	Treatment				EOT	Notes
			Cycle 1		Cycles 2+			
			Day 1	Day 8 (± 3 Days)	Day 15 (± 3 Days)	Day 1 (± 3 Days)		
Serum chemistries	7.5.6	X	X*	X	X	X	X	* May be performed within 3 days of the first dose; screening and Cycle 1 Day 1 can be the same.
Hematology	7.5.6	X	X*	X	X	X	X	* May be performed within 3 days of the first dose; screening and Cycle 1 Day 1 can be the same.
Lipid panel	7.5.6		X				X	
Endocrine	7.5.6	X	X			X	X	
Coagulation panel	7.5.6	X				X*	X	* Only every 3 cycles starting at Cycle 3.
Hepatitis screening	7.5.6	X						
Urinalysis	7.5.6	X				X*		* Only every 3 cycles starting at Cycle 3.
Serum/urine pregnancy	7.5.6.1	X*	X**			X**	X*	* Serum. ** Urine.

Table 6: Local Laboratory Tests: Required Analytes

Serum Chemistries	Hematology	Urinalysis With Microscopic Examination	Hepatitis Screening	Coagulation
Albumin Alkaline phosphatase ALT AST Bicarbonate (not for Japan) Blood urea nitrogen Calcium Chloride Creatinine Glucose Lactate dehydrogenase Phosphate Potassium Sodium Total bilirubin Direct bilirubin (if total bilirubin is elevated above ULN) Total protein Uric acid Vitamin D (25-hydroxyvitamin D and 1,25-dihydroxyvitamin D)	Complete blood count, including: 
 • Hemoglobin • Hematocrit • Platelet count • Red blood cell count • White blood cell count Differential count, including: 
 • Basophils • Eosinophils • Lymphocytes • Monocytes • Neutrophils WBC differential laboratory results: 
 • Lymphocytes • Neutrophils 	Color and appearance pH and specific gravity Bilirubin Glucose Ketones Leukocytes Nitrite Occult blood Protein Urobilinogen	Hepatitis B surface antigen Hepatitis B surface antibody Hepatitis B core antibody HCV antibody NOTE: If any of the above are positive, HBV-DNA, HCV-RNA may be done to assess risk of reactivation if indicated (eg, no history of immunization).	Prothrombin time Partial thromboplastin time (not required in Japan; allow for activated partial thromboplastin time) International normalized ratio
		Lipid Panel	Other	Pregnancy Testing
		Total cholesterol Triglycerides Low-density lipoprotein High-density lipoprotein	Endocrine: PTH	Female subjects of childbearing potential only require a serum test at screening and EOT, and a urine pregnancy test before the first dose on Day 1 of every cycle before dose administration. Pregnancy tests (serum or urine) should be repeated if required by local regulations.

Note: Additional tests may be required, testing schedule may be modified, as agreed by investigator and sponsor, based on emerging safety data.

6.1. Prescreening and Screening

Prescreening is available for subjects without a genomic sequencing report or one that is more than 2 years old. Those subjects will sign a consent form that will allow tissue samples to be sent to the sponsor's central genomic sequencing laboratory. The process takes approximately 2.5 weeks.

Potential subjects can be screened/enrolled based on local genomic sequencing but must have their tumor samples sequenced through the sponsor's central laboratory. The results from the central laboratory will be considered final. In cases where the central laboratory does not show an alteration, the investigator will decide if continuing treatment is in the best interest of the subject; however, the subject will not be included in the efficacy analyses and may be replaced.

Subjects will be assigned to one of 3 cohorts based on central genomic laboratory results and dose regimen:

- Cohort A-ID: FGFR3 mutations or fusions (n = 100); this cohort will complete enrollment before starting the continuous dosing cohort
- Cohort A-CD: FGFR3 mutations or fusions (n = 100)
- Cohort B: all other FGF/FGFR alterations (n = 40; closed at time of Protocol Amendment 5 dated 18 JUN 2018).

Screening is the interval between signing the study ICF and the day the subject is enrolled in the study (Cycle 1 Day 1). Screening may not exceed 28 days. Assessments that are required to demonstrate eligibility may be performed over the course of 1 or more days during the screening process.

Procedures conducted as part of the subject's routine clinical management (eg, blood count, imaging study) and obtained before signing of informed consent may be used for screening or baseline purposes provided the procedure meets the Protocol-defined criteria and has been performed in the time frame of the study (ie, within 28 days of Cycle 1 Day 1). All information associated with eligibility requirements must be entered into the appropriate eCRF pages.

Results from the screening visit evaluations will be reviewed to confirm subject eligibility before enrollment. Tests with results that fail eligibility requirements may be repeated once during screening if the investigator believes the results to be in error. For screening assessments that are repeated, the most recent available result before enrollment will be used to determine subject eligibility. Treatment should start as soon as possible, but within 3 days after the date of enrollment. Additionally, a subject who fails screening may repeat the screening process 1 time if the investigator believes there has been a change in eligibility status (eg, after recovery from an infection). Subjects who are rescreened will receive a new subject number through IRT.

